5.3 Study Visits and Procedures

For each patient, 3 study periods are planned: the screening/enrollment/randomization visit, the 30-day treatment period, and the follow-up period. The procedures and assessments to be performed during each study period are indicated in Table 1. Further relevant details of the evaluations to be performed at each study period are described below.

5.3.1 Screening/Enrollment/Randomization Visit

Before any study-specific activities/procedures, the appropriate written informed consent must be obtained (see section 12.2).

The following procedures will be conducted prior to administration of investigational product (ie, predose):

- Review inclusion/exclusion criteria.
- Confirm positive SARS-CoV-2 molecular or antigen diagnostic test (Note: patient must have a positive SARS-CoV-2 molecular or antigen diagnostic test within 72 hours prior to enrollment).
- Review demographics, medical history, and medication history (including prior [within 90 days before screening/enrollment/randomization visit] and current medications). Date of onset of COVID-19 symptoms should be recorded.
- Perform full physical examination, including measurements of vital signs (blood pressure [mm Hg], respiratory rate [breaths per minute], temperature [°F], and heart rate [beats per minute]), oxygen saturation level, height, weight, and calculation of body mass index.
- Perform urine pregnancy test for females of childbearing potential within 48 hours prior to enrollment.
- Collect nasopharyngeal sample for COVID-19 viral load analysis.
- Provide patient with the eDiary and instruct on usage.
- Provide patient with pulse oximeter and instruct on usage. Instruct patient to seek medical attention immediately should oxygen saturation levels fall to 93% or below.
- Instruct patient on recording severity of COVID-19-related symptoms of cough, dyspnea, chills, and feeling feverish using a 4-point scale where 0 = absent, 1 = mild, 2 = moderate, and 3 = severe, and have patient record baseline results in the eDiary.
- Instruct patient on recording presence/absence of COVID-19-related symptoms of repeated shaking with chills, muscle pain, headache, sore throat, and new loss of taste or smell, and have patient record baseline results in the eDiary.
- Provide patient with study personnel contact information and instruct patient (or their representative) to notify study personnel directly in the event they visit an emergency department or are hospitalized during their participation in the study.
- Dispense investigational product according to treatment assignment.

• Train patient on appropriate MDI inhalation technique and instruct patient to rinse their mouth with water following inhalation of investigational product.

Following completion of the above procedures, study personnel will observe patient self-administration of the first dose of investigational product, and the patient will record administration in the eDiary.

Study personnel will record any adverse events occurring following signing of the informed consent in the eSource direct data capture (DDC) system.

Patients will be instructed to seek medical attention immediately in the event they experience any of the emergency warning signs for COVID-19 as listed on the CDC website.

5.3.2 Double-Blind Treatment Period

- Patient to self-administer investigational product at a frequency of BID (AM [prior to noon] and PM [prior to midnight]) and record in the eDiary.
- Patient to assess severity of COVID-19-related symptoms of cough, dyspnea, chills, and feeling feverish using a 4-point scale at a frequency of BID (AM and PM) ≤ 1 hour prior to investigational product administration and record results in the eDiary.
- Patient to assess presence/absence of COVID-19-related symptoms of repeated shaking with chills, muscle pain, headache, sore throat, and new loss of taste or smell at a frequency of BID (AM and PM) ≤ 1 hour prior to investigational product administration and record results in the eDiary.
- Patient to check oxygen saturation levels using provided pulse oximeter at a frequency of BID (AM and PM) ≤ 1 hour prior to investigational product administration and record in the eDiary.
- Qualified healthcare providers will contact each patient on days 2, 4, 6, 8, 10, 12, 14, 21 ± 2 days, and 30 ± 2 days for a health status check, to collect adverse event and concomitant medication information, and to confirm/clarify information recorded in the eDiary. During these patient contacts, medical advice commensurate with standard of care for reported symptoms or adverse events will be provided.
- Patient to return to the study site on day 30 (window of + 2 days) for collection of nasopharyngeal sample for viral load analysis and to return the eDiary and investigational product (ie, used and unused MDIs).

Note on day 1 dosing: In the event the patient receives the initial dose of investigational product at or before noon during the screening/enrollment/randomization visit, this will be considered to be the day 1 AM dose and the patient will be instructed to perform symptom assessments and oxygen saturation level monitoring, and to self-administer the day 1 PM dose prior to midnight. In the event the patient receives the initial dose of investigational product any time after noon during the screening/enrollment/randomization visit, this will be considered to be the day 1 PM dose and the patient will be instructed to wait until morning to perform symptom assessments, oxygen saturation level monitoring, and to self-administer the next dose (ie, day 2 AM dose).

Note on day 30 dosing: Patients will be instructed to continue dosing through day 30. In the event the patient has their day 30 (window of + 2 days) visit on day 30, they will be instructed to perform symptom assessments and oxygen saturation level monitoring, and to self-administer the day 30 doses as per their typical schedule/routine. Thus, depending upon the time of day that the day 30 visit occurs, patients may or may not receive both doses on day 30. For patients that have their day 30 visit on day 31 or day 32, they will be instructed to complete through the day 30 PM dose and then discontinue investigational product dosing, symptom assessments, and oxygen saturation level monitoring.

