4.3.1 Primary Endpoint Estimand

The attributes of the estimand for the primary endpoint of this trial are:

- 1. Treatment regimens: ciclesonide and placebo
- 2. Populations of interest: patients meeting inclusion/exclusion criteria grouped according to randomized treatment assignment reflect the target population
- Patient-level outcome: time to alleviation of COVID-19-related symptoms of cough, dyspnea, chills, feeling feverish, repeated shaking with chills, muscle pain, headache, sore throat, and new loss of taste or smell, defined as symptom-free for a continuous period of ≥ 24 hours (ie, ≥ 3 AM/PM assessments) by day 30
- 4. Intercurrent events: regardless of the use of rescue medications, protocol violations, or investigational product discontinuation
- 5. Population-level summary measure: difference in survival distributions between treatment regimens

The **treatment-policy strategy** for this estimand is the difference in survival distributions of time to alleviation of COVID-19-related symptoms of cough, dyspnea, chills, feeling feverish, repeated shaking with chills, muscle pain, headache, sore throat, and new loss of taste or smell, defined as symptom-free for a continuous period of ≥ 24 hours (ie, ≥ 3 AM/PM assessments) by day 30 between those assigned to ciclesonide and those assigned to placebo, regardless of patient's use of rescue medications, protocol violations, or investigational product discontinuation. Therefore, for all patients in the intent-to-treat (ITT) analysis set, all observed on-study data will be analyzed in accordance with the definition set forth above for intercurrent events.

Since death and hospitalization are not part of the primary endpoint patient level-outcome definition, a composite strategy will be used to handle these situations. If a patient dies or is hospitalized, regardless of when it occurs, the value attributed in that scenario would be a failure to respond or achieve alleviation of COVID-19-related symptoms by the end of the study (day 30). This ascribes a sufficiently unfavorable outcome under these scenarios.

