7.1.2 Efficacy Assessments

7.1.2.1 Assessment of COVID-19-Related Symptoms of Cough, Dyspnea, Chills, and Feeling Feverish

Patients will assess severity of COVID-19-related symptoms of cough, dyspnea, chills, and feeling feverish using a 4-point scale where 0 = absent, 1 = mild, 2 = moderate, and 3 = severe. Assessment of these symptoms will be performed predose during the screening/enrollment/ randomization visit. During the 30-day treatment period, patients will be instructed to assess these 4 symptoms using a 4-point scale at a frequency of BID prior to self-administration of the investigational product (ie, within 1 hour of administration). The patient will record results in the eDiary.

7.1.2.2 Presence/Absence of COVID-19-Related Symptoms of Repeated Shaking with Chills, Muscle Pain, Headache, Sore Throat, and New Loss of Taste or Smell

Patients will assess the presence/absence of COVID-19-related symptoms of repeated shaking with chills, muscle pain, headache, sore throat, and new loss of taste or smell. Assessment of these symptoms will be performed predose during the screening/enrollment/randomization visit. During the 30-day treatment period, patients will be instructed to assess presence/absence of these symptoms at a frequency of BID prior to self-administration of the investigational product (ie, within 1 hour of administration). The patient will record results in the eDiary.

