9.2.3 Action Taken with Investigational Product

For each recorded adverse event, the action taken with investigational product will be documented as follows:

- No change
- Drug interrupted
- Drug withdrawn
- Not applicable
- Unknown

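### Symptom entries are timed to doses, and the protocol does not say whether they continue off product, although the primary estimand counts patients regardless of discontinuation

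*Combined protocol and SAP*

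**What the plan says.** Section 5.3.2 schedules both sets of symptom ratings "at a frequency of BID (AM and PM) ≤ 1 hour prior to investigational product administration and record results in the eDiary". Section 7.1.2.1 has the four graded symptoms rated "at a frequency of BID prior to self-administration of the investigational product (ie, within 1 hour of administration"; section 7.1.2.2 does the same for the present/absent symptoms. Section 5.1 and Table 1 agree.

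The same sections also carry a calendar element. Section 7.1.2.1 opens with "During the 30-day treatment period, patients will be instructed to assess these 4 symptoms using a 4-point scale", Table 1 places the entries in day 1 through day 30, and section 5.3.2 defines AM as before noon and PM as before midnight.

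The endpoint in section 4.3.1 is "defined as symptom-free for a continuous period of ≥ 24 hours (ie, ≥ 3 AM/PM assessments) by day 30". Product discontinuation is handled by treatment policy: patients count "regardless of the use of rescue medications, protocol violations, or investigational product discontinuation", and "all observed on-study data will be analyzed in accordance with the definition set forth above for intercurrent events". Section 4.3.2 treats the key secondary endpoint in the same way.

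Section 9.2.3 lists "Drug interrupted" and a drug-withdrawn category among the actions taken for an adverse event, so a patient can be off product without having left the study. Section 6.4 covers only withdrawal from the study.

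**The concern.** A treatment-policy estimand needs outcome data after product is stopped. Here the outcome comes from a twice-daily diary, and the only stated moment for an entry is the hour before a dose. A patient who has interrupted or stopped product has no such moment and no instruction on whether to go on. A recovered patient who skips doses may also skip the entries that would document recovery. Sites and patients could reasonably act in different ways.

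The data at stake carry most of the early testing sequence. The first four endpoints in section 10.7.3 use the symptom diary. The fifth, oxygen saturation at day 7, uses readings that section 5.3.2 also ties to a dose. Entries that are not made cannot be recovered at the analysis stage.

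**Working it through.** **1. What happens to entries when dosing stops**

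| Situation | What the protocol says |
|---|---|
| Day 30 visit held on day 31 or 32 (5.3.2) | Patients "complete through the day 30 PM dose and then discontinue investigational product dosing, symptom assessments, and oxygen saturation level monitoring" |
| Hospitalisation (5.1) | Product and scheduled follow-up procedures stop together |
| Early termination (5.3.4) | eDiary and product are both returned |
| Dose skipped, product interrupted or product stopped, patient still in the study | No statement that entries continue or that they cease |

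The last row is the gap. Hospitalised patients are outside it, because section 4.3.1 counts them as failures under a composite strategy.

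**2. Power**

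Inputs from section 10.1: hazard ratio 1.58, medians 7 and 11 days, 30 days, 201 events, 400 patients.

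- Plan's figure (Schoenfeld, two-sided 0.05, 90% power, 1:1): 4 × (1.960 + 1.282)² / (ln 1.58)² ≈ 201 events. This reproduces the plan.
- Event probability by day 30, exponential: 1 − 2^(−30/7) = 0.949 and 1 − 2^(−30/11) = 0.849; mean 0.899.
- Expected events in 400 patients: 400 × 0.899 ≈ 360.
- Share that can be lost before the count reaches 201: 1 − 201/359.5 = 0.44.
- Power at hazard ratio 1.58 is 98.4% if 10% of events are lost, 97.3% if 20% are lost and 91.9% if 40% are lost.

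**3. Bias (illustration; stopping rates are assumptions)**

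Set-up: true hazard ratio 1, both medians 11 days, entries stop at a uniformly distributed time on days 1 to 10, and patients whose entries stop before alleviation count as not alleviated at day 30. Simulation used 200,000 patients per arm, with a hazard ratio approximated from daily intervals.

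| Stopping, ciclesonide / placebo | Apparent hazard ratio |
|---|---|
| 10% / 10% | 1.00 |
| 5% / 15% | 1.13 |
| 10% / 20% | 1.13 |
| 20% / 10% | 0.89 |

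A value above 1 favours ciclesonide. Direction and size depend on the missing-data rule, which is not in the supplied text. In this set-up stopping is unrelated to recovery time, so censoring at the last entry would introduce no bias.

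**4. Delay from skipped entries (assumption-based)**

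Assume that misses are independent, each missed dose is a missed entry, and a missed entry breaks the run of three. With entry probability q, the expected number of entries needed is (1 − q³) / ((1 − q)q³). Subtract 3 and divide by 2 entries per day:

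- q = 0.9: 3.72 entries, 0.36 day
- q = 0.8: 4.77 entries, 0.88 day
- q = 0.7: 6.39 entries, 1.69 days

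None of the three assumptions, and none of the q values, comes from the documents.

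**The case against.** The strongest objection is that the schedule has a calendar frequency as well as a dose anchor. Entries are due twice daily over a 30-day period, and AM and PM are defined by the clock. On that reading the one-hour rule only fixes the order when a dose is taken, and a patient off product still owes both entries. This stands. A reader might infer that off-product patients have no scheduled entry and that their recovery is never recorded. The documents do not support that; they are silent, and the text can be read either way.

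A reader might also set the delays in step 4 against the planned 4-day difference in medians. That is not like for like: a similar delay in both arms moves both medians and leaves their difference largely intact.

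There are mitigations. Nine provider contacts confirm or clarify eDiary data and check compliance, and section 10.7.1 commits to a tipping-point analysis. These reduce the consequence but do not close the gap. The contacts are not described as a symptom assessment, and after day 14 they fall only around days 21 and 30, so they cannot supply three AM/PM assessments over 24 hours. A tipping-point analysis varies assumptions about missing outcomes; it does not recover them.

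**Conclusion.** The concern holds as an omission. The protocol does not say whether or when symptom entries continue in a patient who is off product but still in the study, while both described estimands count that patient regardless of discontinuation. Entries may be lost as a result.

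Bias in time to alleviation is possible if stopping or skipping differs by arm. Its size cannot be fixed from the documents, which give no discontinuation rate and leave missing-data handling to the SAP. The apparent hazard ratios of 0.89 to 1.13 rest on assumed stopping rates and on counting missing patients as not alleviated; they show what could happen and are not an estimate. Loss of power is a minor issue. The point merits correction because the data cannot be collected afterwards and the change is cheap.

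**What to change.** In sections 5.1, 5.3.2, 7.1.2.1 and 7.1.2.2 and Table 1 (and the synopsis, which repeats 5.1), tie symptom entries to the existing AM (before noon) and PM (before midnight) windows, made before the dose when a dose is taken. Do the same for the oxygen entries in 5.3.2 and Table 1, so that they agree with 7.1.2.3, which already sets a twice-daily frequency without a dose anchor. Then add:

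*AM and PM entries continue through day 30 whether or not a dose is taken, including after interruption or discontinuation of investigational product in patients who remain in the study and are not hospitalised; these patients keep the eDiary until the day 30 visit.*

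The SAP should state how a missing entry affects the run of three and how patients whose entries stop are handled.

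The cost is a short amendment with aligned wording, an eDiary prompt setting, and slightly more diary burden for patients off product. It adds no visits and changes no dose or clinical rule.

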5.3.3 Follow-Up Period

• Qualified healthcare providers to contact patient to collect follow-up safety and outcome data on day 37 ± 4 days and day 60 ± 7 days.

5.3.4 Early Termination Procedures

In the event of early termination, all ongoing non-serious adverse events will be followed until resolution, stabilization, or study day 60, whichever comes first; all ongoing serious adverse events will be followed until resolution or resolution with sequelae. Patients should be instructed to return the eDiary and investigational product (ie, used and unused MDIs) to the study site in a timely manner.

6 PATIENT ELIGIBILITY AND WITHDRAWAL CRITERIA

6.1 Number of Patients

Approximately 400 patients (200 in each arm) will be randomized. A sample size justification is provided in section 10.1.

It is anticipated that patients will be enrolled at up to 15 study sites in the United States.

6.2 Inclusion Criteria

Patients eligible for enrollment in the study must meet all the following criteria:

- 1. Male and female adults and adolescents ≥ 12 years of age.
- 2. Positive SARS-CoV-2 molecular or antigen diagnostic test within 72 hours prior to enrollment.
- 3. Patient is not currently hospitalized or under immediate consideration for hospitalization at the time of enrollment.
- 4. Patient is currently experiencing symptoms of fever, cough, and/or dyspnea.
- 5. Patient has an oxygen saturation level > 93%.
- 6. Ability to show adequate use of MDI, including inhalation technique.
- 7. Patient, parent/legal guardian, or legally-authorized representative must have signed a written informed consent before administration of any study-specific procedures. In the event the patient is a minor under the age of 18, assent by the patient to participate in the study must also be obtained.

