3 INTRODUCTION

3.1 Background Information on Coronavirus Disease 2019 (COVID-19)

There is currently an outbreak of respiratory disease caused by a novel coronavirus that was first detected in Wuhan City, Hubei Province, China, and that has now been detected in many locations internationally, including cases in the United States. The virus has been named Severe Acute Respiratory Syndrome Coronavirus 2 (SARS-CoV-2) and the disease it causes has been named Coronavirus Disease 2019 (COVID-19). On January 31, 2020, the Department of Health and Human Services issued a declaration of a public health emergency related to COVID-19 and on March 13, 2020, the President declared a national emergency in response to COVID-19.

The United States Centers for Disease Control and Prevention (CDC) has stated that symptoms compatible with COVID-19 include subjective or measured fever, cough, or difficulty breathing, and may present within 2 to 14 days after exposure. Reported illnesses have ranged from mild symptoms to severe illness and death for confirmed COVID-19 cases.

Currently there are no approved treatments for COVID-19. Innovators are looking at products in a variety of areas, including the assessment of antiviral drugs that might treat the specific virus, as well as host targets, such as interleukin-6 receptor inhibitors that may be helpful in reducing lung inflammation and improving lung function in COVID-19 patients, thereby potentially slowing the progression of severe respiratory symptoms.

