7 STUDY ASSESSMENTS AND PROCEDURES

7.1 Efficacy

7.1.1 Efficacy Endpoints

The primary efficacy endpoint is:

• Time to alleviation of COVID-19-related symptoms of cough, dyspnea, chills, feeling feverish, repeated shaking with chills, muscle pain, headache, sore throat, and new loss of taste or smell, defined as symptom-free for a continuous period of ≥ 24 hours (ie, ≥ 3 AM/PM assessments) by day 30

The secondary efficacy endpoints for the study are:

- Percentage of patients with hospital admission or death by day 30
- All-cause mortality by day 30
- COVID-19-related mortality by day 30
- Percentage of patients with subsequent emergency department visit or hospital admission for reasons attributable to COVID-19 by day 30
- Percentage of patients with alleviation of COVID-19-related symptoms of cough, dyspnea, chills, feeling feverish, repeated shaking with chills, muscle pain, headache, sore throat, and new loss of taste or smell, defined as symptom-free for a continuous period of ≥ 24 hours (ie, ≥ 3 AM/PM assessments) by day 7, by day 14, and by day 30
- Time to hospital admission or death
- Change from baseline in oxygen saturation levels
- Change from baseline in COVID-19 viral load in nasopharyngeal sample at day 30

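### No baseline eDiary rating is required for entry, so a patient can be randomized with all nine endpoint symptoms absent and count as an early recovery on either arm; the effect is mild dilution

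*Combined protocol and SAP*

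**What the plan says.** Protocol section 6.2, criterion 4, and the synopsis require: "Patient is currently experiencing symptoms of fever, cough, and/or dyspnea". The criterion gives no severity threshold or temperature cut-off and does not mention the eDiary.

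Section 7.1.1 builds the primary endpoint on nine symptoms: "cough, dyspnea, chills, feeling feverish, repeated shaking with chills, muscle pain, headache, sore throat, and new loss of taste or smell". Alleviation is "defined as symptom-free for a continuous period of ≥ 24 hours (ie, ≥ 3 AM/PM assessments) by day 30". The day-7, day-14 and day-30 responder endpoints use the same definition.

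Under section 5.3.2 the fever-type item is rated by the patient twice daily: "Patient to assess severity of COVID-19-related symptoms of cough, dyspnea, chills, and feeling feverish using a 4-point scale". At the first visit (section 5.3.1) the site is to "have patient record baseline results in the eDiary", once for the scored items and once for the present/absent items. Temperature is taken in the physical examination at that visit ("respiratory rate [breaths per minute], temperature [°F], and heart rate [beats per minute") and is not among the eDiary items.

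Sections 10.2 and 10.7.1 put every randomized patient in the primary analysis. Section 10 leaves further statistical detail to an SAP whose text is not in the documents available for this review.

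**The concern.** Entry and endpoint are decided by different people on different records. The site applies criterion 4; the patient fills in the eDiary. Three routes are open to a patient who is eligible but has all nine items absent at baseline:

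- a raised temperature that the patient does not feel;
- fever reported to the site, while the patient's own rating of feeling feverish at that moment is 0;
- any other disagreement between the site's judgement and the patient's ratings on cough or dyspnea.

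Time to alleviation has no clear meaning for such a patient, because nothing is present at time zero. As written, the patient stays in the ITT set and meets the event definition almost at once, whichever kit was assigned. Section 10.7.3 tests the primary endpoint first and the day-14, day-7 and day-30 responder endpoints next, so the first four tests in the fixed sequence would all carry these treatment-independent successes. What is at stake is dilution of the estimated effect and an endpoint that is not well defined for everyone randomized.

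**Working it through.** **1. Entry rule and endpoint side by side**

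| | Criterion 4 | Endpoint and eDiary |
|---|---|---|
| Fever | *fever*, felt or measured not specified | *feeling feverish*, rated 0 to 3 |
| Cough, dyspnea | included | included, rated 0 to 3 |
| Other six symptoms | not used | included |
| Source | site eligibility review | patient's own rating |
| Minimum baseline rating | none | none |

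Section 3.1 speaks of "symptoms compatible with COVID-19 include subjective or measured fever, cough, or difficulty breathing", so the protocol recognises both kinds of fever. Two of the three entry symptoms match endpoint items outright, and the third matches whenever the fever is felt. The gap that remains is the missing link between eligibility and the patient's baseline ratings.

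**2. When such a patient becomes an event**

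The definition needs three consecutive absent AM/PM assessments spanning 24 hours. The protocol does not say whether the predose rating counts as one of them.

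- Predose rating counts, morning start: day 1 AM, day 1 PM, day 2 AM.
- Predose rating does not count, afternoon start: day 2 AM, day 2 PM, day 3 AM.

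The event therefore falls at about day 2 to 3.

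**3. Reproducing the protocol's sample size**

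Inputs from section 10.1: medians 7 and 11 days, hazard ratio about 1.58, 30 days, 90% power, alpha 0.05 (two-sided reproduces; one-sided gives 164 events).

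- Schoenfeld: 4 × (1.960 + 1.282)² / (ln 1.58)² = 201 events, as stated.
- Exponential event probability by day 30: 1 − 2^(−30/7) = 0.949 and 1 − 2^(−30/11) = 0.849, mean 0.899.
- 201 / 0.899 = 224 patients. Freedman's formula gives 208 events, and 208 / 0.899 rounds up to the stated 232.

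**4. Dilution by direct calculation**

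Let f be the share in each arm with no endpoint symptom at baseline. The documents give no value, so f is an assumed range. With exponential times for the rest, the median solves (1 − f) × 2^(−t/m) = 0.5, so t = m × log2[2(1 − f)]. The day-14 responder difference without such patients is 75.0% − 58.6% = 16.4 points, and it scales by (1 − f).

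| f | Median, ciclesonide | Median, placebo | Difference | Day-14 difference |
|---|---|---|---|---|
| 0 | 7.0 | 11.0 | 4.0 days | 16.4 points |
| 5% | 6.5 | 10.2 | 3.7 days | 15.6 points |
| 10% | 5.9 | 9.3 | 3.4 days | 14.8 points |

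**5. Simulation**

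Unadjusted log-rank test, half-day grid, censoring at day 30, no dropout, a share f in each arm given an event at 24 hours, 3,000 trials per setting. Hazard ratios are one-step log-rank estimates.

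| f | Hazard ratio | Power, N = 400 | Power, N = 232 |
|---|---|---|---|
| 0 | about 1.60 | 99% | 90% |
| 5% | about 1.56 | 98% | 88% |
| 10% | about 1.52 | 97% | 83% |

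The one-step estimate starts slightly above 11/7 = 1.571. A separate simulation under the same assumptions started at 1.58 and gave 1.53 and 1.49, a shift of similar size. With no treatment difference, f = 5% and N = 232, the rejection rate was 5.2%. With 3,000 trials its Monte Carlo error is √(0.05 × 0.95 / 3,000) = 0.4 points, so this shows no inflation.

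**The case against.** The best case for leaving the protocol alone has four parts.

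First, criterion 4 is worded as something the patient experiences. A patient experiencing fever would ordinarily rate feeling feverish at 1 or more, and cough and dyspnea carry straight over. This stands. A reader might infer that fever lies outside the endpoint and the eDiary altogether; the documents do not support that, because feeling feverish is in both.

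Second, the failure needs an unusual patient: all nine items absent at baseline, and still absent over the following assessments. A symptom that returns as an antipyretic wears off breaks the run. Under section 4.3.1, a patient who is hospitalized or dies is a failure whatever the diary shows. This also stands, and no figure in the documents suggests a share of 5% or 10%.

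Third, the numbers are small and the bias is toward no effect. The increase from 232 to 400 patients was made partly for unnamed factors that could affect power. This stands as far as power is concerned. It does not make the endpoint well defined for a patient with nothing to alleviate.

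Fourth, the SAP may contain an analysis rule, and section 5.3.1 already lists the baseline eDiary recordings before dispensing. The first part cannot be ruled out. However, an SAP rule acts after randomization, so it could remove such patients only by departing from the all-randomized primary analysis. On the second part, the listing does not make the rating an entry condition. Table 1 places randomization above the symptom ratings, and both are marked only as predose.

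**Conclusion.** The point holds as a minor, low-cost improvement. No provision in the protocol ties entry to a present symptom in the patient's own baseline record. A patient with none of the nine would be counted as an early, treatment-independent recovery in the first four tests of the fixed sequence, unless a symptom appears first or the hospitalization and death rule applies.

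The size is modest: hazard ratio about 1.60 falling to 1.56 at an assumed 5% and 1.52 at 10%, with power at 400 patients about 97% or more. These figures rest on exponential times with the protocol's medians, an equal share in both arms, no dropout and an unadjusted test; the planned analysis is a covariate-adjusted Cox model. The share itself is an assumption. That it is probably small is a judgement from the need for all nine items to be absent.

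A reader might infer that the planned power or the validity of the primary test is in danger. The calculations do not support this: power stays above the 90% target at the planned size, and dilution does not create false positives. Nor can one conclude that no analysis rule exists, since the SAP text was not available.

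**What to change.** Add to criterion 4, in section 6.2 and the synopsis, that at least one of the nine symptoms in section 7.1.1 is recorded as present (score of 1 or more, or marked present) in the predose eDiary assessment. State in section 5.3.1 and Table 1 that this rating is completed before a kit is assigned.

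The cost is wording and the fixed order of one step; the rating is already taken predose at the same visit. The downside is an occasional screen failure.

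If the entry rule is left as it is, the SAP should state how patients with all nine items absent at baseline are analysed and whether the predose rating counts toward the three assessments. It should add a sensitivity analysis without these patients. That is the weaker remedy, because they would still be in the primary ITT analysis.
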